#### 7.7.2. Change from baseline in mean total score, individual subscale scores, and loudness score

- *Computation of the Endpoint*

The change from baseline to each post-baseline visit will be computed as  $w - b$  where “w” is the post-baseline score and “b” is the score at baseline.

- *Analysis of the Endpoint*

The change from baseline to each post-baseline visit in mean total TFI score, individual subscale scores, and loudness score will be summarized descriptively by visit and treatment group for subjects in the FAS.

For subjects in the FAS, treatment group comparisons for the change from baseline in mean total TFI score will be analyzed using a mixed-effect, repeated measures model using fixed covariates for treatment group, WR score at baseline (<50% versus ≥50%), etiology of hearing loss (SSNHL versus NIHL), visit, and interaction between visit and treatment group. The covariance structure (UN or AR(1)) that provides the best model fit for the TFI total score, as described in Section 7.7.1, will be implemented with a repeated statement in SAS. The treatment group differences analyzed will be between each FX-322 group (including the pooled FX-322 group) versus placebo, and comparisons between the individual FX-322 groups (excluding the pooled FX-322 group). Comparisons will be made by visit (e.g., estimated LS Mean differences by visit) and overall (e.g., Type III Sums of Squares). The analysis will be repeated for the loudness score.

Correlation analyses between the mean change from baseline in total TFI score, individual subscale scores, and the loudness score versus the following WR, WIN and PTA continuous endpoints for treated ears will be performed for subjects in the FAS:

- WR:

- Percentage of recognized words (Section 7.3.2)
- Absolute percent change from baseline in word recognition (Section 7.3.3)
- Relative percent change from baseline in word recognition (Section 7.3.4)
- Arcsine-transformed word recognition (Section 7.3.6)
- WIN:
  - Percentage of recognized words (Section 7.4.2)
  - Absolute percent change from baseline in word recognition (Section 7.4.3)
  - Relative percent change from baseline in word recognition (Section 7.4.4)
  - Median Spearman-Kärber estimates of dB thresholds for word recognition (Section 7.4.6)
- PTA:
  - Mean overall PTA (AC over 0.5, 1, 2, and 4 kHz) (Section 7.5.5)

Pearson correlation coefficients for the specified correlations will be summarized by visit and treatment group for subjects in the FAS.

Scatter plots will also be used to display the correlations. The change from baseline in TFI score (total, subscale, or loudness) will be plotted on the x-axis and the efficacy endpoint (WR, WIN, PTA) for treated ears will be plotted on the y-axis, with a separate plot for each post-baseline visit. Treatment groups will be differentiated using different symbols.

Post hoc correlation analyses may be performed on select qualitative WR, WIN and PTA endpoints of interest.

## 7.8. Hearing Handicap Inventory for Adults

The HHIA is a 25-item self-assessment scales composed of two subscales (13 items for Emotional and 12 items for Social/Situational). All items are on a 3-level scale of 0 to 4 (No = 0, Sometimes = 2, Yes = 4). The total and subscale scores range from 0 (no handicap) to 100 (total handicap) and will be computed as the sum of item response scores for each scale divided by the maximum possible score for the scale. The total and subscale scores will be missing if any item response scores are missing. The subject will complete the assessment (either directly onto the questionnaire in person, via web, or over the phone) at the Day 1, 60, 120, and 210 visits.

Baseline scores for analysis will be computed from the Day 1 visit. No imputation will be performed for missing data and no sensitivity analyses will be performed for the HHIA endpoints.

### 7.8.1. Mean total score and individual subscale scores

- *Computation of the Endpoint*

At each visit, the mean total HHIA score will be computed as the sum of all item responses and divided by 100. The Emotional and Social/Situational scores will be the sum of all subscale items, divided by the maximum possible score (52 for Emotional and 48 for Social/Situational).

- *Analysis of the Endpoint*

The mean total HHIA score and individual subscale scores will be summarized descriptively by visit and treatment group for subjects in the FAS.

For subjects in the FAS, treatment group comparisons for the mean total HHIA score will be analyzed using a mixed-effect, repeated measures model using fixed covariates for treatment group, WR score at baseline (<50% versus ≥50%), etiology of hearing loss (SSNHL versus NIHL), visit, and interaction between visit and treatment group. As described in Section 7.3.4, separate models will be fit specifying UN and AR(1) covariance structures (implemented with a repeated statement in SAS). The covariance structure providing the lowest corrected AICc and BIC values from the model will be implemented for the HHIA total score and all other HHIA endpoints. The treatment group differences analyzed will be between each FX-322 group (including the pooled FX-322 group) versus placebo, and comparisons between the individual FX-322 groups (excluding the pooled FX-322 group). Comparisons will be made by visit (e.g., estimated LS Mean differences by visit) and overall (e.g., Type III Sums of Squares). The analysis will be repeated for each HHIA subscale score.

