#### **14.1.5 Efficacy Exploration**

Efficacy endpoints will be summarized descriptively at each study timepoint including baseline. Calculations will include the observed data at each timepoint, and if relevant, the change from baseline. For continuous endpoints means, medians, standard deviations, minimums and maximum will be provided. For categorical endpoints the number and percent of subjects within each category will be calculated. Tabulations for selected endpoints will be presented by subgroups such as age, study site, duration of hearing loss, smoking status, and stratification factors used at randomization. Details will be provided in the SAP. For descriptive analyses, subjects with missing data will be excluded for a particular calculation.

For questionnaires, the analysis will follow the instructions for scoring and handling of missing data appropriate for the particular instrument.

Inferential statistical methods examining continuous endpoints will be examined via a Mixed Model for Repeated Measures (MMRM). Analyses will include pairwise contrasts and dose response. Inferential analyses for categorical endpoints will be analysed using univariate methods and/or Generalized Linear Mixed Models (GLMM). When appropriate, models will include adjustments for baseline as well as the stratification factors used at randomization. Departures of these models from the statistical assumptions will be assessed and alternative approaches maybe employed. Additionally, univariate models such as Analysis of Covariance and/or count models examining single timepoints of interest may also be examined. General methods for handling missing data for inferential analyses are described below (Section 14.2).

The inferential analyses will not be adjusted for multiple endpoints; however, for a given endpoint, adjusted p-values for pairwise comparisons to a control will be provided where

relevant along with the unadjusted p-values. Unadjusted 95% confidence intervals will also be provided. In some circumstances, adjusted confidence intervals may be calculated.

Efficacy endpoints will be analysed using the FAS. Further details regarding the exploratory analysis of efficacy will be outlined in the SAP.

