#### 7.8.2. Change from baseline in mean total score and individual subscale scores

- *Computation of the Endpoint*

The change from baseline to each post-baseline visit will be computed as  $w - b$  where “w” is the post-baseline score and “b” is the score at baseline.

- *Analysis of the Endpoint*

Descriptive summaries, treatment group comparisons, and correlation analyses will be performed for change from baseline in mean total HHIA score and change from baseline in mean HHIA subscale scores as described in Section 7.7.2. The covariance structure identified in Section 7.8.1 will be utilized.

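### Neither HHIA model adjusts for the subject's own Day 1 HHIA score, which costs precision and leaves the comparison open to chance baseline imbalance

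*SAP*

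**What the plan says.** SAP 7.8 has the HHIA completed "at the Day 1, 60, 120, and 210 visits" and states: "Baseline scores for analysis will be computed from the Day 1 visit". It plans no HHIA sensitivity analyses.

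SAP 7.8.1 compares the arms on the HHIA total and subscale scores with a repeated-measures model using "fixed covariates for treatment group, WR score at baseline (<50% versus ≥50%), etiology of hearing loss (SSNHL versus NIHL), visit" and the visit-by-treatment interaction.

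SAP 7.8.2 says that "treatment group comparisons, and correlation analyses will be performed for change from baseline in mean total HHIA score". It extends this to "change from baseline in mean HHIA subscale scores as described in Section 7.7.2. The covariance structure identified in Section 7.8.1 will be utilized". The 7.7.2 model has the same list of terms, with no questionnaire score among the covariates.

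Protocol 14.1.5 says: "When appropriate, models will include adjustments for baseline as well as the stratification factors used at randomization". SAP Section 11, which records changes from the protocol, mentions only the dropped multiplicity adjustment.

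Protocol 7.2 lists HHIA among the additional exploratory efficacy endpoints, as a mean change.

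**The concern.** A subject's self-rated handicap before treatment is likely to be the best single predictor of the same rating afterwards. The only baseline quantity in the models is the word-recognition stratum, a two-level split of a score from one ear, whereas the HHIA is a 25-item report about the whole person. The raw-score model leaves all between-subject variation in handicap, beyond what the strata explain, in the error term. The change model uses the Day 1 score, but fixes its coefficient at one instead of estimating it.

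With 24 subjects per arm and no stratification on HHIA, the arms can differ on Day 1 by chance. The two planned models carry that difference into the treatment contrast in opposite directions, and the SAP does not say which one to read. In an exploratory study the estimates and intervals are the product, so noise that could be removed with data already collected matters.

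**Working it through.** **Is baseline HHIA in either model?** The lists in 7.8.1 and 7.7.2 contain treatment, word-recognition category, etiology, visit and visit by treatment. Neither contains a baseline HHIA term. The SAP does not say whether Day 1 is a response level in 7.8.1. If it is, the unconstrained visit-by-treatment term still gives essentially raw differences at each follow-up visit. Only a model holding the arms equal on Day 1 would recover the precision, and none is specified.

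**Could the word-recognition term be the baseline that the protocol means?** No. Protocol 8.7.3 makes it a stratification factor, and 14.1.5 names baseline in addition to those factors.

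**Inputs.** From the documents: 24 per arm, 1:1:1:1 allocation, 95% intervals. Assumed, because the documents give no value: equal SD at Day 1 and follow-up; correlation rho of 0.5, 0.7 or 0.8 between them after allowing for the strata; a true difference of 0.5 SD; all 24 per arm observed. The plan has no power or precision figure to reproduce, since the sample size was not formally derived.

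**Formulas** (per-subject variance in SD units, one follow-up visit):
- raw score: 1
- change score: 2(1 − rho)
- adjusted for Day 1: 1 − rho²
- SE = sqrt(variance × 2/24)
- power = P(Z > 1.96 − 0.5/SE)

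Example at rho 0.7: change SE = sqrt(0.60 × 2/24) = 0.224, so power = P(Z > 1.96 − 2.24) = 61%. Adjusted SE = sqrt(0.51 × 2/24) = 0.206, so power = P(Z > 1.96 − 2.42) = 68%.

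| rho | SE raw | SE change | SE adjusted | Power raw | Power change | Power adjusted |
|---|---|---|---|---|---|---|
| 0.5 | 0.289 | 0.289 | 0.250 | 41% | 41% | 52% |
| 0.7 | 0.289 | 0.224 | 0.206 | 41% | 61% | 68% |
| 0.8 | 0.289 | 0.183 | 0.173 | 41% | 78% | 82% |

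**Gain over the change model.** The SE ratio is sqrt((1 − rho²)/(2(1 − rho))) = sqrt((1 + rho)/2) = 0.87, 0.92 and 0.95, or about 11, 7 and 4 power points. At rho 0.7, 24 adjusted subjects per arm are worth 24 × 2/1.7 = 28 analysed by change.

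**Gain over the raw-score model.** About 11, 27 and 41 points.

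**Chance imbalance.** The Day 1 difference between two arms has SD sqrt(2/24) = 0.289 SD units. Given a Day 1 difference d, the raw comparison shifts by rho × d and the change comparison by (rho − 1) × d. At rho 0.7 and d = 0.289 these are +0.20 and −0.09, so the two planned answers differ by the full 0.29. The adjusted comparison does not shift.

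**Do the strata already do the work?** In a simulation of 3,000 trials (four arms of 24, two binary strata as covariates, strata explaining 10% of score variance, overall correlation 0.7), adding the Day 1 score cut the variance to 0.86 of the change model and 0.55 of the raw model. With zero correlation, and strata explaining nothing, the ratio to the raw model was 1.01, so a useless baseline would cost almost nothing.

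**Where one visit is all there is.** SAP Section 10 includes HHIA in the interim analysis and excludes data after Day 90. Day 60 is then the only scheduled post-baseline HHIA visit, so the single-visit calculation fits that analysis directly.

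**The case against.** The best reply is that the endpoint is a mean change and 7.8.2 already models change, so the Day 1 score is used where it matters. This stands in part. It makes the change model the fair comparator, with a gain of 4 to 11 power points; a reader who takes the 41-point figure as the loss would be measuring against a model that does not match the endpoint. If handicap ratings are very stable, the gain over change is at its smallest.

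Three stronger readings are tempting and are not supported:
- *The change analysis is biased by regression to the mean.* Subjects are not selected on HHIA, and under randomisation any such regression is expected equally in every arm. It matters only given a chance imbalance, which is the same precision point again.
- *The SAP breaches the protocol.* The protocol sentence applies when appropriate and leaves further detail to the SAP, and modelling change is one way of taking account of baseline. What can be said is that the SAP gives no reason for leaving the covariate out.
- *Nothing tells the reader which model governs.* The SAP states no order, but the protocol endpoint points to change.

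It is also true that no decision rests on HHIA: there is no single primary endpoint, and all p-values are descriptive.

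**Conclusion.** The omission is real and applies to both HHIA models. Its effect is lower precision and exposure to chance Day 1 imbalance, not bias on average. Against the change model, adjustment reduces the SE by about 5 to 13% over assumed correlations of 0.8 down to 0.5; against the raw-score model the loss is larger. These sizes rest on an assumed correlation, equal SDs and complete data at the visit. The direction does not depend on the correlation chosen: apart from about one degree of freedom, the adjusted model is never less precise than either planned one. Because HHIA is an additional exploratory endpoint, this is worth correcting but does not threaten a study conclusion.

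**What to change.** In SAP 7.8.2, add the Day 1 value of the matching HHIA score (total, Emotional or Social/Situational) as a continuous covariate, preferably with a baseline-by-visit term. Keep the two stratification factors and state that only post-baseline visits are responses, so that Day 1 is not both outcome and covariate. Name this as the model for HHIA treatment comparisons, and keep the 7.8.1 raw scores as descriptive summaries. A second inferential model would be redundant, because with the same Day 1 covariate, subjects and terms, raw and change outcomes give the same treatment contrast. The covariance selection now placed in 7.8.1, and the HHIA rows of Table 7-2, would move accordingly. If the covariate is left out on purpose, say why in Section 11.

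The cost is some SAP wording and one degree of freedom, or three with baseline by visit over Days 60, 120 and 210. No subject is lost relative to the change model, which already needs a Day 1 score. Subjects without a valid Day 1 score would drop out of the HHIA comparison relative to the raw-score model, and SAP 7.8 sets a score to missing if any of its items is missing. The TFI and HSI models use the same covariate list and could be considered at the same time.

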#### 7.8.2. Change from baseline in mean total score and individual subscale scores

- *Computation of the Endpoint*

The change from baseline to each post-baseline visit will be computed as  $w - b$  where “w” is the post-baseline score and “b” is the score at baseline.

- *Analysis of the Endpoint*

Descriptive summaries, treatment group comparisons, and correlation analyses will be performed for change from baseline in mean total HHIA score and change from baseline in mean HHIA subscale scores as described in Section 7.7.2. The covariance structure identified in Section 7.8.1 will be utilized.

#### 7.9. Hearing Screening Inventory

The HSI is a 12-item questionnaire assessing hearing impairment. Items 1 to 8 are scored on a 5-point ordinal scale: Never = 1, Seldom, Occasionally, Frequently, and Always = 5. Items 9 to 12 are on different 5-point scale: Good = 1, Average, Slightly Below Average, Poor, Very Poor = 5. The total score is on a 0 to 60 scale and is the sum of all 12 response scores, with items 2, 3, 4, 7, and 8 being reverse-scored (inverted). The total score will be missing if any item response scores are missing. Lower scores are favorable and higher scores are unfavorable. The HSI is designed to assess subjective change during the study and will be given to the subject to complete at the Day 1 and 210 visits.

Baseline scores for analysis will be computed from the Day 1 visit. No imputation will be performed for missing data and no sensitivity analyses will be performed for the HSI endpoints.

### 7.9.1. Mean total score

- *Computation of the Endpoint*

At each visit, the mean total HSI score will be computed as the sum of all 12 responses scores. Items 1, 5, 6, 9, 10, 11, and 12 will maintain the original 5-point scoring and items 2, 3, 4, 7, and 8 will be reverse-scored (inverted). The total score is on a 0 to 60 scale.

- *Analysis of the Endpoint*

The mean total HSI score will be summarized descriptively by visit and treatment group for subjects in the FAS.

For subjects in the FAS, treatment group comparisons for the mean total HSI score will be analyzed using a mixed-effect, repeated measures model using fixed covariates for treatment group, WR score at baseline (<50% versus ≥50%), etiology of hearing loss (SSNHL versus NIHL), visit, and interaction between visit and treatment group. As described in Section 7.3.4, separate models will be fit specifying UN and AR(1) covariance structures (implemented with a repeated statement in SAS). The covariance structure providing the lowest corrected AICc and BIC values from the model will be implemented for the HSI total score and all other HSI endpoints. The treatment group differences analyzed will be between each FX-322 group (including the pooled FX-322 group) versus placebo, and comparisons between the individual FX-322 groups (excluding the pooled FX-322 group). Comparisons will be made by visit (e.g., estimated LS Mean differences by visit) and overall (e.g., Type III Sums of Squares).

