| Urine Pregnancy Test (women of child bearing potential only) | X               | X b         | X b                        |                                    |                                     | X i       |
| Urine Drug Screen  | X a  |                        |                                       |                                    |                                     |                      |
| Safety Laboratory Assessments                                | X               |                        |                                       |                                    | X h                      | X i       |
| Blood sample for biomarker analysis                          |                 | X b         |                                       |                                    | X h                      |                      |
| Study Medication (FX-322 or placebo)                         |                 | X                      | X                                     |                                    |                                     |                      |
| Adverse Events   |                 | X c         | X b, c                     | X                                  | X                                   | X                    |

- a- See exclusion regarding positive drug tests
- b- Assessment performed prior to injection.
- c- Assessments performed after injection.
- d- Perform only at Day 15 visit.
- e- Visit windows: +/- 2 days for treatment visits, +/- 15 days for follow up visits.
- f- Subjects will be administered questionnaires over the phone or the internet depending on site's preference.
- g- Perform only at Day 60, 120, and 210 visits.
- h- Perform only at Day 210 visit.
- i- Perform at Investigator Discretion

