### **11.2.4 Hearing Screening Inventory (HSI)**

The Hearing Screening Inventory is a 12 item self report inventory to assess hearing impairment. The subject will self report one of the following answers, for each question from 1 to 8: Never, Seldom, Occasionally, Frequently, Always, and for each question from 9 to 12: Good, Average, Slightly below average, Poor, Very Poor. The HSI is designed to assess subjective change during the study and will be given to the subject to complete at the Baseline and Day 210 visits.

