### 7.9.2. Change from baseline in mean total score

- *Computation of the Endpoint*

The change from baseline to each post-baseline visit will be computed as  $w - b$  where “w” is the post-baseline score and “b” is the score at baseline.

- *Analysis of the Endpoint*

Descriptive summaries, treatment group comparisons, and correlation analyses will be performed for change from baseline in mean total HSI score as described in Section 7.7.2. The covariance structure identified in Section 7.9.1 will be utilized.

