## 10. INTERIM ANALYSIS AND DATA MONITORING

The blinded data will be continuously monitored for safety. Interventional level aggregated data monitoring will be conducted once all enrolled subjects have completed the Day 90 visit (Visit 5) or were early discontinuations. An interim analysis of all Day 90 data may be performed to assist in data interpretation or to understand patterns of missingness in real-

time or to monitor data integrity. The study will continue as planned to final analysis when all patients have completed their day 210 visit.

The planned interim analysis will include select tables and figures planned for the CSR, with subjects grouped into randomized or actual treatment groups based on unblinded treatment assignments. Datasets supporting the select tables and figures will also be provided along with the raw randomization codes. In the tables and figures, model results and descriptive statistics through Visit 5 (Day 90) will be presented, as appropriate. With the exception of the subject disposition summary and Kaplan-Meier plot of time from the date of randomization to the date of study completion or early discontinuation, all data after Day 90 will be excluded.

The following tables and figures planned for the CSR analyses are planned for the IA: Subject Disposition for Consented subjects (Section 5.1), Demographic and Baseline Characteristics for the FAS (Section 5.2), Subject Visit Accountability for the FAS (Section 5.1), WR, WIN, and Audiometry accountability (Section 7.1.6), Major Protocol Deviations for Randomized Subjects (Section 6.1), Study Treatment Exposure for the FAS (Section 8.2), Word Recognition in Quiet for the FAS and PPS excluding analyses by site or subgroup (Section 7.3), Words-In-Noise for the FAS and PPS excluding analyses by site or subgroup (Section 7.4), Pure Tone Audiometry analyses for the FAS and PPS (Section 7.5), Composite Endpoint for the FAS and PPS (Section 7.5.9), TFI for the FAS (Section 7.7), HHI for the FAS (Section 7.8), HSI for the FAS (Section 7.9), Adverse Events for the SfAS (Section 8.3), Otoscopic Examination for the SfAS (Section 8.6.3), Tympanometry for the SfAS (Section 8.6.4), C-SSRS for the SfAS (Section 8.6.5), and concomitant medications for the SfAS (Section 8.6.6). Phoneme analyses, WR and WIN analyses by site or subgroup, as well as any sensitivity analyses for the FAS due to study treatment administration in the not qualified ear are excluded from the IA.

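### The HSI has one scheduled post-dose visit (Day 210) and none by Day 90, so its repeated-measures model, covariance selection, overall test and interim listing do not fit the data; a Day 210 ANCOVA on baseline HSI would

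*SAP*

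**What the plan says.** **Schedule.** Protocol 11.2.4 states that the HSI "will be given to the subject to complete at the Baseline and Day 210 visits". In the Protocol 8.1.2 schedule, the HSI entry for in-clinic follow-up carries the footnote "h- Perform only at Day 210 visit", and the SAP 13.2 schedule agrees. SAP 7.9 says the HSI "will be given to the subject to complete at the Day 1 and 210 visits" and adds: "Baseline scores for analysis will be computed from the Day 1 visit".

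**Model.** SAP 7.9.1 specifies a mixed repeated-measures model for the total score. Its fixed effects are treatment, dichotomised baseline word recognition, etiology, visit and visit-by-treatment. For the covariance, "separate models will be fit specifying UN and AR(1) covariance structures", with the choice made on AICc and BIC. Arms are compared at each visit and overall, with Type III sums of squares given as the example for the latter. For change from baseline, SAP 7.9.2 follows the approach of 7.7.2 and says: "The covariance structure identified in Section 7.9.1 will be utilized". Neither section includes baseline HSI as a covariate.

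**Interim.** SAP Section 10 lists "TFI for the FAS (Section 7.7), HHI for the FAS (Section 7.8), HSI for the FAS (Section 7.9") among the planned interim outputs. The same section excludes data after Day 90 from everything except disposition and the Kaplan-Meier plot, and SAP 7.1.5 sets the same limit for models and descriptive summaries.

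**The concern.** With Day 1 as baseline, each subject has one scheduled post-dose HSI value. A model with visit terms, a choice of within-subject covariance and a test across visits presupposes several. The SAP does not say whether Day 1 enters the 7.9.1 model as a response, and the meaning of the overall test depends on that choice. A programmer could settle it either way.

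Both documents describe the HSI as a measure of subjective change during the study. Three things are at stake: an overall test that is either redundant or diluted by a pre-dose visit, precision lost because the Day 1 score is collected but not used as a covariate, and unblinded interim tables that could show HSI arm comparisons with no scheduled post-dose data behind them.

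**Working it through.** The documents give no HSI effect size, standard deviation, correlation or power, so there is no planned figure to reproduce.

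**1. Count of visits.** Scheduled HSI visits: Day 1 and Day 210, so 2 in total. Post-dose: 1. Post-dose by Day 90: 0.

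**2. Covariance parameters for T modelled visits.** UN has T(T+1)/2 parameters. AR(1) has 2 if T is at least 2, but only its variance is identifiable if T = 1.

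| Modelled visits | UN | AR(1) |
|---|---|---|
| T = 1 (Day 210 only) | 1 | 1 identifiable |
| T = 2 (Day 1 and Day 210) | 3 | 2 |

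**3. Day 210 only.** This is unavoidable for change from baseline in 7.9.2, and is one reading of 7.9.1. The two structures are the same model. A numerical check on simulated data with 96 subjects gave the same log-likelihood (-120.309) at AR(1) correlations of 0.0001, 0.3, 0.6 and 0.9. The design-matrix rank for treatment was 4 with or without the visit and interaction terms. There is nothing to select, and the overall comparison is the Day 210 comparison.

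**4. Day 1 as a response in 7.9.1.** Selection is now possible. Assume equal variances (set to 1), correlation r between Day 1 and Day 210, a treatment difference d at Day 210, and zero expected difference at Day 1 because of randomization. For a pairwise contrast, with variances given up to a common factor:

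- Visit-averaged (main effect): effect d/2, variance (1+r)/2.
- Day 210, unadjusted: effect d, variance 1.
- Ratio of z-values: 0.5/√((1+r)/2) = 1/√(2(1+r)).

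At r = 0.5 this is 1/√3.0 = 0.58; at 0.7, 1/√3.4 = 0.54; at 0.8, 1/√3.6 = 0.53.

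As an illustration, take 24 per arm, two-sided 0.05 and an assumed effect of 0.8 SD. Power for the visit-averaged contrast is 0.36 at r = 0.5 and 0.32 at r = 0.7, against 0.79 for the Day 210 contrast.

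**5. Adjustment for baseline HSI, a separate question.** Under the same assumptions, ANCOVA has effect d with variance 1-r², and the change score has effect d with variance 2(1-r).

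- Unadjusted Day 210 relative to ANCOVA: √(1-r²).
- Change score relative to ANCOVA: √((1-r²)/(2(1-r))) = √((1+r)/2).

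| z-value ratio | r = 0.5 | r = 0.7 | r = 0.8 |
|---|---|---|---|
| Visit-averaged / unadjusted Day 210 | 58% | 54% | 53% |
| Unadjusted Day 210 / ANCOVA | 87% | 71% | 60% |
| Change score / ANCOVA | 87% | 92% | 95% |

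**6. Interim.** Only Day 1 is scheduled by Day 90. Scheduled data therefore give no change from baseline and no correlation with change, and any arm comparison of total score compares pre-dose values.

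**The case against.** The strongest reply is that valid HSI analyses are already in the plan. SAP 7.9.1 asks for comparisons by visit, and the Day 210 contrast is undiluted whether or not Day 1 is a response. SAP 7.9.2 adds change from baseline, which loses only 5% to 13% of the ANCOVA z-value over the assumed correlations. The SAP does not say which Type III term the overall comparison uses; with Day 1 as a response, the visit-by-treatment term tests change and is not halved. All of this stands. It confines the halving to one implementation and one term.

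Three stronger readings are tempting, and the documents do not support them.

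- *That the overall test should be measured against ANCOVA*, which would give 50%, 39% and 32%. Those figures multiply the dilution in step 4 by the baseline-adjustment gain in step 5. The SAP does not plan that ANCOVA, and the missing own-baseline covariate is not peculiar to HSI: the WR, WIN, PTA, TFI and HHIA models have the same covariates.
- *That interim HSI tables can hold only pre-dose scores.* The schedule allows unscheduled HSI at the investigator's discretion, Protocol 8.4.4 encourages withdrawing subjects to complete the final evaluations, and SAP 7.1.2 maps such efficacy data to visits. A few post-dose values by Day 90 are possible, though too sparse to support a repeated-measures model. The accurate statement is that no *scheduled* post-dose HSI exists by then.
- *That covariance selection also fails for TFI and HHIA at the interim.* The SAP selects their structure on total scores, which exist at Day 1 and Day 60, and then reuses it for change. The selection step could run if Day 1 is a response.

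Section 10 also presents interim results as appropriate, which could permit a baseline-only HSI table, but it does not say that this is intended. No stated decision depends on the table.

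**Conclusion.** The point holds as a minor mismatch between schedule and model. The visit counts come straight from the documents and need no assumption. With Day 210 alone, covariance selection and the overall test are empty. With Day 1 as a response, an overall treatment main effect has half the expected Day 210 effect and 53% to 58% of the z-value of the planned Day 210 contrast. That size assumes equal variances, correlations of 0.5 to 0.8 and no expected pre-dose difference.

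The loss from not conditioning on baseline HSI is distinct: 13% to 40% of the ANCOVA z-value for the unadjusted Day 210 contrast, and 5% to 13% for the change score. The planned HSI analyses are not invalid as a whole; the by-visit Day 210 contrast and the change analysis both stand.

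Severity is low because HSI is an additional exploratory endpoint (Protocol 7.2), there is no single primary endpoint (SAP 7.2), and all p-values are descriptive (SAP 7.1.4).

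**What to change.** - **SAP 7.9.1 and 7.9.2:** replace the two mixed models with one ANCOVA of Day 210 HSI on treatment, baseline (Day 1) HSI and the two stratification factors. With baseline HSI as a covariate, modelling Day 210 score or change gives the same treatment difference, so one model serves both sections. Keep the descriptive summaries.
- **SAP 7.9.1, 7.9.2, 7.1.5 and Table 7-2:** delete the UN/AR(1) selection and the overall test for HSI, and add ANCOVA to the model types in 7.1.5. Protocol 14.1.5 already provides for baseline adjustment where appropriate and for ANCOVA at single timepoints, so this stays within the protocol.
- **SAP Section 10:** remove HSI from the interim list, or state that it is limited to a baseline summary without arm comparisons.

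The cost is SAP wording and simpler code. No new data are needed, since the Day 1 score is already collected.
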